8.3 Treatment Assignment

Treatment will be conducted in an open label manner. The eCRF will assign a subject number identifier for each subject that is enrolled into the study. Study sites cannot start dosing the subject without receiving the assigned subject number.

8.7 Blinding

This is an open label study with no placebo or comparators.

8.8 Treatment Compliance

The importance of treatment compliance should be emphasized to the subject. Subjects will be given study drug and detailed instructions on how to take medications at home. Subjects will be instructed to return all used and unused study drug containers at each study visit. Subject compliance with the dosing schedule will be assessed by reconciliation of the used and unused study drug at each clinic visit and review of the dosing diaries. The quantity dispensed, returned, used, lost, etc. must be recorded on the Drug accountability log provided.

Compliance will be monitored and documented by site personnel on the appropriate form. The site personnel will question the subject regarding adherence to the dosing schedule by reviewing the dosing diaries, recording the number of tablets (and strengths, if applicable) returned, the date returned, and determining treatment compliance (at least 80% of the total assigned dose) before dispensing new medication to the study subject.

46 of 89

8.14 Potential Effects on Reproduction and Development

Male and female fertility and reproductive capacity has been shown to be impaired in rats and additional details can be found in the Tipifarnib Investigator's Brochure.

In light of the observations in nonclinical testing, both female subjects and male subjects with female partners of child-bearing potential must agree to use a highly effective method of contraception for 2 weeks prior to screening, during, and at least 4 weeks after last dose of trial medication. Female subjects of child-bearing potential must have a negative serum or urine pregnancy test within 72 hours prior to start of trial medication.

Additionally, since tipifarnib could induce toxicity of male reproductive organs and cause impairment of fertility, sperm cryopreservation should be recommended for male subjects

wishing to preserve their fertility following tipifarnib treatment. Additionally, if the participant in the study is male, then the following items will be discussed with the subject:

- Prevention of pregnancy in a female partner
- Prevention of exposure of a partner to semen by any means (not just intercourse)
- Prevention of the possible exposure of a pregnant female to the study drug from semen.
- Informing their partner of the potential for harm to an unborn baby. The partner should know that if pregnancy occurs, she should promptly notify her personal doctor.
- Acceptable methods of birth control for male subjects while participating in this study and for 4 weeks after the last dose of the study drug:
 - Abstinence (no sex)
 - Condom plus spermicidal agent (foam gel/cream/film/suppository)

8.15 Medical Care of Subjects after End of Trial

After a subject has completed the trial or has withdrawn from the study, standard treatment will be administered, if required, in accordance with the trial site's standard of care and generally accepted medical practice and according to the subject's individual medical needs.

9 EFFICACY AND SAFETY VARIABLES

Table 1 summarizes the study required evaluations.

9.1 Efficacy Variables

Radiological and/or physical assessments of the tumor lesions will be made at screening (4 weeks before the first study drug administration), and approximately every 8 weeks for the first 6 months (cycles 2, 4, 6) and then every 12 weeks (cycles 9, 12, 15, etc.) until disease progression, starting at the end of Cycle 2. Additional tumor assessments may be conducted if deemed necessary by the Investigator or for a confirmation of an objective response. Subjects who discontinue treatment for reasons other than disease progression must continue tumor assessments until disease progression, withdrawal of their consent to study procedures or initiation of another anticancer therapy. Efficacy assessments may also be conducted at treatment discontinuation (End of Treatment visit) if the reason for the treatment termination is other than disease progression and a tumor assessment was not done within 8 weeks before

treatment discontinuation (assessment must be conducted before additional anti-tumor therapy is started). Scans at the End of Treatment visit will be also conducted if required to confirm response to treatment.

Lesions to be included in the tumor assessments should follow RECIST v1.1 criteria (Appendix II). Spiral CT scan with a contrast agent is the preferred imaging method. Tumor assessment with spiral CT scans of the abdomen, pelvis and chest plus other relevant evaluations, e.g. bone scans, should be performed as appropriate. Subjects with contrast allergy may use non-contrast CT or MRI, whichever is required to adequately assess all disease.

Objective response (complete response and partial response) as determined by the subject's best tumor response, duration of response, and time to progression will be assessed using RECIST criteria version 1.1. Confirmation of response is required.

In addition to Investigator's tumor response assessment, a central independent review tumor response assessment may be performed if the Sponsor deems it necessary for the final assessment of the efficacy of the treatment. If an independent radiological review were to be conducted, reviewers will be blinded to the Investigator's efficacy assessments. The Sponsor, in consultation with the investigators, may initiate this independent review at any time during the trial. In that case, an independent review committee charter would be generated to provide the specific procedures that would be filed with IRBs/IECs and regulatory authorities prior to their initiation.

Upon disease progression, all subjects will be followed approximately every 12 weeks for survival and the use of subsequent therapy until either death or 24 months after accrual in the subject's study cohort has been completed, whichever occurs first. Information on survival and subsequent anticancer therapy may be collected by phone.

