The treatment phase will investigate the antitumor activity in terms of ORR of tipifarnib in subjects with locally advanced squamous non-small cell lung cancer (SQ-NSCLC) with HRAS mutations and for whom there is no curative therapy available. Subject enrolment may proceed with information available on tumor HRAS status previously generated during the pre-screening phase, but all subjects must consent to provide tumor slides (or tumor tissue block) from a prior diagnostic biopsy for a retrospective testing of RAS gene status, including T81C polymorphism, and other potential biomarkers at a central facility.

Tipifarnib will be administered at a starting dose of 600 mg, po, bid daily on days 1-7 and 15-21 of 28-day treatment cycles. In the absence of unmanageable toxicities, subjects may continue to receive tipifarnib treatment for up to 24 months in the absence of disease progression and unmanageable toxicity. Treatment may continue beyond 24 months if there is documented evidence of continued clinical benefit.

Tumor assessments will be performed at screening and approximately every 8 weeks for the first 6 months (cycles 2, 4, 6) and then every 12 weeks (cycles 9, 12, 15, etc.) until disease progression, starting at the end of Cycle 2. Additional tumor assessments may be conducted if deemed necessary by the Investigator or for a confirmation of an objective response. Subjects who discontinue tipifarnib treatment for reasons other than disease progression must continue tumor assessments until disease progression, withdrawal of subject's consent to study procedures or initiation of another anticancer therapy.

Determination of objective tumor response will be performed by the Investigator according to the Response Evaluation Criteria in Solid Tumors (RECIST) v 1.1 (Appendix II). Electronic copies of tumor images may be de-identified of subject's personal information at the clinical sites and collected by the Sponsor to undergo an external independent radiological review if the sponsor deems it necessary for the final assessment of treatment efficacy. Subjects with a solitary site of disease who have experienced a response may be considered for surgical resection. Subjects with a best response of a partial response and residual disease after salvage surgery will be eligible to continue on study therapy. Information on the duration of response to the last prior therapy will be collected.

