11.1 Populations

11.1.1 Efficacy Analysis

The FAS population will serve as the primary population for the analysis of tumor response and other efficacy-related data. Subjects will be excluded for FAS for the following reasons:

- No baseline data
- Failure to receive at least one dose of tipifarnib
- No post-baseline endpoint data subsequent to at least 1 dose of study drug

A supportive analysis using the Per-Protocol population will be performed for the tumor response analysis. The Per-Protocol population excludes subjects due to important deviations from the protocol that may substantially affect the results of the primary analysis, such as not taking at least 80% of the intended dose in cycle 1. The final determination on protocol violations, and thereby the composition of the Per-Protocol population, will be made prior to locking the clinical database and final analysis and will be documented in a separate memorandum.

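### The baseline scan can satisfy the 8-week look-back for the End of Treatment scan, so a subject who stops early and switches therapy can have no post-baseline scan and leave the FAS

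*Combined protocol and SAP*

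**What the plan says.** Section 9.1 makes the End of Treatment scan optional. It may be done "if the reason for the treatment termination is other than disease progression and a tumor assessment was not done within 8 weeks before" discontinuation, and before any further anti-tumor therapy. The look-back is not limited to post-baseline assessments.

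The screening scan belongs to the same series. Section 9.1 says: "Radiological and/or physical assessments of the tumor lesions will be made at screening (4 weeks before the first study drug administration". The Synopsis says: "Tumor assessments will be performed at screening and approximately every 8 weeks for the first 6 months (cycles 2, 4, 6". The first scan on treatment comes at week 8 ("starting at the end of Cycle 2"). After cycle 6 the plan is "then every 12 weeks (cycles 9, 12, 15, etc.) until disease progression".

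Subjects who stop for reasons other than progression must go on being scanned, but only until they progress, withdraw consent to procedures or start another anticancer therapy. Separate sentences let the investigator add scans and require an End of Treatment scan where one is needed to confirm a response.

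Section 11.1.1 makes the FAS the primary population for tumor response. One ground for exclusion is "No post-baseline endpoint data subsequent to at least 1 dose of study drug". The Synopsis (Statistical Methods) defines an evaluable subject differently: tissue HRAS missense status, a baseline scan and one day of dosing. It asks for no post-baseline scan.

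**The concern.** The useful purpose of an End of Treatment scan in an early stopper is to obtain one post-baseline assessment before the subject moves on. As worded, the condition asks only whether any scan is recent, and before week 8 the baseline scan is the only one on schedule. A subject can then stop for toxicity or by choice, switch therapy before week 8, and never be scanned on or after treatment.

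Such a subject has no documented response. Removal from the FAS shrinks the denominator and leaves the numerator alone, so the FAS response rate can only rise. With 18 subjects planned, each one is more than 5% of the denominator. The same subject is evaluable for the design but outside the primary analysis population.

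**Working it through.** **Inputs.** Cycles last 28 days (Synopsis: "on days 1-7 and 15-21 of 28-day treatment cycles"). The baseline scan falls B days before first dose, with B from 0 to 28 (section 9.1, reading the 4 weeks as a maximum). On-schedule scans fall on days 56, 112, 168 and 252 (ends of cycles 2, 4, 6 and 9). The look-back is 56 days. Let d be the day treatment stops.

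**1. The plan's own figures.** The scan rule carries none, so the check is on the design it feeds (section 11.3): 7 subjects, stop on 0 responses, then 11 more, success at 4 or more of 18. The probability of success is the sum over x = 1 to 7 of P(X1 = x) × P(X2 ≥ 4 − x), with X1 ~ Bin(7, p) and X2 ~ Bin(11, p).

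- p = 0.10: 0.0893 (stated 0.089).
- p = 0.30: 0.8000 (stated 80%).

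Both reproduce.

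**2. When the condition is met.** It is met if d − (day of latest scan) > 56. Before day 56 the latest scan is the baseline, so the test is d + B > 56.

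- Cycle 1: the largest value is 28 + 28 = 56, which is not greater than 56. It is never met.
- Cycle 2: it is met only when d > 56 − B.

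| Baseline, days before dosing | Stop days before week 8 that meet the condition |
|---|---|
| 28 | 29–55 |
| 21 | 36–55 |
| 14 | 43–55 |
| 7 | 50–55 |
| 0 | none |

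- Days 56–168: on the 8-week grid the latest scan is at most 56 days old, so it is never met. Here the on-treatment scans satisfy the look-back, not the baseline.
- Days 169–251: it is met on days 225–251 (168 + 57 = 225).

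**3. With the look-back limited to post-baseline scans.** Every stop on days 1–55 meets the condition. Nothing changes from day 56 on.

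**4. Effect on the FAS analysis.** Suppose k unscanned subjects leave the FAS and 4 subjects respond. The documents give no early-stop rate, so k = 1 to 3 is an assumption. The rate is 4/(18 − k). The p-value is P(X ≥ 4) for X ~ Bin(18 − k, 0.10). The interval is the exact (Clopper-Pearson) 90% interval, an assumed method because section 11.2.1 does not name one.

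| k | FAS ORR | 90% CI | One-sided exact p vs 10% |
|---|---|---|---|
| 0 | 4/18 = 22.2% | 8.0–43.9% | 0.098 |
| 1 | 4/17 = 23.5% | 8.5–46.1% | 0.083 |
| 2 | 4/16 = 25.0% | 9.0–48.4% | 0.068 |
| 3 | 4/15 = 26.7% | 9.7–51.1% | 0.056 |

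The relative inflation is 18/(18 − k): 1.06, 1.13 and 1.20.

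**The case against.** **The main source of the bias is section 11.1.1, not 9.1.** This is right. If unscanned treated subjects stayed in the denominator as non-responders, the inflation would vanish without any extra scan. Changing 9.1 alone would still lose subjects who die, refuse the scan or withdraw consent. The fix therefore needs both parts.

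**Other provisions may supply a scan.** Investigators may add scans, and subjects who do not switch therapy are still due the week 8 scan. The loss is confined to early stoppers without progression who start another therapy, or withdraw consent, before that scan and get no discretionary scan. That limits the number but does not close the gap.

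**The look-back could run from the End of Treatment visit.** Section 7.4 places that visit within about 30 days of the last dose. With B = 28, a day 1 stop and a visit 30 days later, the gap is 28 + 31 = 59 days and the condition is met. With B = 14 it is 45 days and is not. Section 7.4 also brings the visit forward when another therapy is about to start, which is the case at issue. The cycle 1 result in the working counts from the stop itself. On either reading the scan is only optional.

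**Stronger readings that the documents do not support.**

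- A reader might infer that one lost subject takes the result below 0.089 and turns failure into success. The 0.098 and 0.083 are single-stage tail probabilities, while 0.089 is the level of the two-stage design. Under section 11.3, 4 of 18 is already a success, and the unscanned subject can still be among the 18 evaluable.
- A reader might infer that the trial's type I error rises. If lost subjects were replaced until 18 FAS subjects were reached, the null rate in the FAS would be 0.10/(1 − q). The chance of success would then be 0.120 at an assumed loss of q = 10% and 0.165 at 20%. The available text contains no such replacement rule, and the evaluable definition points the other way.
- A reader might count the untriggered weeks 8–24 as part of the problem. Subjects who stop then already have the week 8 scan, if on schedule, and are not lost from the FAS by this route.

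**Conclusion.** The point holds as a limited one. Counted from the day treatment stops, the condition for the End of Treatment scan is never met in cycle 1 and is met only in part of cycle 2, or not at all, depending on the baseline date. Combined with the FAS exclusion, this can remove early stoppers who switch therapy from the primary response analysis.

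The bias in the FAS response rate, its interval and the exact test is upward. Its size is about 1.3 percentage points for one assumed loss and 2.8 for two, at 4 responders. The go/no-go count is not itself altered.

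The conclusion rests on three assumptions: that endpoint data in section 11.1.1, which is undefined, means tumor assessments and not survival; that lost subjects have no documented response; and that no instruction elsewhere overrides 9.1. The last cannot be confirmed. Most of Table 1 and all of section 7.2 are absent from the public text, and section 11 defers details of the primary analysis to the SAP.

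**What to change.** 1. In section 9.1, make the look-back refer to post-baseline tumor assessments only.
2. In the same place, state that the scan will be done, before any other anticancer therapy, for every subject with no post-baseline scan. Step 1 alone is not enough while the scan remains optional.
3. In section 11.1.1, keep treated subjects who have a baseline scan but no post-baseline scan in the response-rate denominator as non-responders. This covers deaths, refusals and withdrawals of consent, which no scan rule can reach, and aligns the FAS more closely with the evaluable definition.
4. Check that Table 1 and section 7.2 agree with the revised text.

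The cost is a few words in two sections, an occasional extra scan at a visit the protocol already holds, and a slightly lower FAS response rate where early stoppers occur.

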1 SYNOPSIS

TITLE: An Open Label Phase II Study of Tipifarnib in Advanced Squamous Non-small Cell Lung Cancer with HRAS mutations

SPONSORS: Fundación GECP

PROTOCOL NUMBER: THOMAS (GECP 17/04)

KURA CODE: KO-IST-003

STUDY SITES: 30 centers in Spain

PHASE OF DEVELOPMENT: Phase II

STUDY PERIOD: This trial is planned to initiate enrolment in the first half of 2017. It is estimated that it may require approximately 3 years to complete all its study objectives.

OBJECTIVES:

Primary Objective: To determine the antitumor activity in terms of objective response rate (ORR) of tipifarnib in subjects with locally advanced unresectable or metastatic, relapsed and/or refractory, squamous non-small cell lung cancer (SQ-NSCLC) with HRAS mutations. This objective will be evaluated in the treatment phase of the study.

Secondary Objective 1: To determine the frequency of HRAS mutations in squamous non-small cell lung cancer (SQ-NSCLC). This objective will be evaluated in the pre-screening phase of the study.

Secondary Objective 2: Safety and tolerability of tipifarnib in subjects with locally advanced unresectable or metastatic, relapsed and/or refractory, squamous non-small cell lung cancer (SQ-NSCLC) with HRAS mutations. This objective will be evaluated in the treatment phase of the study.

Exploratory Objective 1: To explore the antitumor activity in terms of progression free survival (PFS) and duration of response (DOR) of tipifarnib in subjects with locally advanced unresectable or metastatic, relapsed and/or refractory, squamous non-small cell lung cancer (SQ-NSCLC) with HRAS mutations. This objective will be evaluated in the treatment phase of the study.

Exploratory Objective 2: To explore the identification of biomarkers potentially related to tipifarnib activity in tumor tissue and/or cell free DNA. This objective will be evaluated in the treatment phase of the study.

STUDY DESIGN:

This Phase II study consists of 2 parts: 1) pre-screening phase and 2) treatment phase.

The pre-screening phase will investigate the presence of HRAS mutations in subjects with a histologically or cytologically confirmed diagnosis of squamous non-small cell lung cancer (SQ-NSCLC). Subjects may participate in the pre-screening phase at initial diagnosis or following prior lines of therapy for SQ-NSCLC.

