5.3 Exploratory Objective and Endpoints

Exploratory Objective 1: To explore the antitumor activity in terms of progression free survival (PFS) and duration of response (DOR) of tipifarnib in subjects with locally advanced unresectable or metastatic, relapsed and/or refractory, squamous non-small cell lung cancer (SQ-NSCLC) with HRAS mutations. This objective will be evaluated in the treatment phase of the study.

Exploratory Endpoints 1: PFS and DOR according to RECIST 1.1.

Exploratory Objective 2: To explore the identification of biomarkers potentially related to tipifarnib activity in tumor tissue and/or cell free DNA. This objective will be evaluated in the treatment phase of the study.

Exploratory Endpoints 2: Molecular analyses of archival tissue samples.

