6.1.2 Treatment Phase

For inclusion of a subject in the treatment phase, all of the following inclusion criteria must be fulfilled:

- 1. Subject has a histologically or cytologically confirmed diagnosis of squamous non-small cell lung cancer (SQ-NSCLC) for which there is no curative therapy available.
- Subject has relapsed (progressive disease) or is refractory to one or more prior therapies. In the case of therapy received in the adjuvant or neo-adjuvant setting, relapse must have occurred within 12 months to be considered prior therapy. Subject may have received prior immunotherapy.
- 3. Subject has a tumor that carries a missense HRAS mutation. HRAS status may have been assessed either in primary tumor tissue, recurrent or metastatic disease.
- 4. Subject has consented to provide tumor slides (or tumour tissue blocks) for biomarker evaluation. Before enrolment the site must confirm the availability of the tumor sample. If there is no sample available, the trial chair must be contacted for approval. If enrolment in the treatment portion of the study has taken place based on HRAS mutant status as

assessed using a blood sample, tumor tissue must be sent before starting cycle 2 of treatment, and It will be used in part for confirmation of HRAS mutant tumor status. Confirmation of HRAS mutant status in tumor tissue is required for continuation of treatment. If HRAS mutation is not confirmed in tumor but is clearly positive in blood, the trial chair will be contacted for approval and the treatment could be maintained. All treated subjects will be evaluated for safety.

- 5. Subject has measurable disease according to RECIST v1.1.
- 6. At least 2 weeks since the last systemic therapy regimen prior to enrolment. Subjects must have recovered to NCI CTCAE v. 4.03 < Grade 2 from all acute toxicities (excluding Grade 2 toxicities that are not considered a safety risk by the Sponsor and Investigator) or toxicity must be deemed irreversible by the Investigator.

- 7. At least 2 weeks since last radiotherapy. If radiation was localized to the only site of measurable disease, there must be documentation of disease progression of the irradiated site. Subjects must have recovered from all acute toxicities from radiotherapy. Subjects may be on a daily dose of corticosteroids (≤ 20mg prednisone or equivalent), as part of their management from prior radiotherapy.
- 8. ECOG performance status of 0 or 1.
- 9. Acceptable liver function:

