11.2 Endpoints

11.2.1 Efficacy

The efficacy endpoints are listed in section 5. Up to 18 subjects will be enrolled in the treatment phase of this study. The primary endpoint is overall response rate (ORR) at 6 months, which will be compared to historical control via exact binomial test in comparison to historical control ORR 10%. Binary response endpoints will be summarized by counts and percents of subjects. Traditional 90% confidence intervals for TRUE underlying rates will also be computed and reported.

Correlation of responses with biomarkers will be assessed via comparisons of distributions of biomarkers among various categories of the response endpoints, to be defined in the SAP.

Additional categories of response may be defined and assessed based on the observed data during exploratory analyses.

Summary statistics will be provided for other endpoints.

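### Section 9.1 lists time to progression where the synopsis and section 5.3 specify PFS; align the terms and state how deaths without progression are handled

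*Combined protocol and SAP*

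**What the plan says.** The first exploratory objective in section 5.3 is "To explore the antitumor activity in terms of progression free survival (PFS) and duration of response (DOR) of tipifarnib", and the matching endpoint line reads "Exploratory Endpoints 1: PFS and DOR according to RECIST 1.1". The synopsis states the same objective.

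Section 9.1 (Efficacy Variables) lists best tumor response and then "duration of response, and time to progression will be assessed using RECIST criteria version 1.1". PFS is not mentioned there.

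The statistical section does not repeat the list. Section 11.2.1 says "The efficacy endpoints are listed in section 5" and, for everything other than the primary endpoint, "Summary statistics will be provided for other endpoints".

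Three other provisions bear on the point:

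- **Scan timing (9.1).** The first scheduled scan after baseline is at the end of Cycle 2, which is week 8 with 28-day cycles. The interval later widens to 12 weeks.
- **Analysis population (11.1.1).** The full analysis set (FAS) leaves out subjects without endpoint data after baseline.
- **Survival follow-up (9.1).** It is described as starting at progression: "Upon disease progression, all subjects will be followed approximately every 12 weeks for survival and the use of subsequent therapy".

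**The concern.** One section names a different time-to-event variable from the section that defines the endpoints. The difference has content. Under the usual definitions PFS ends at progression or death, whichever comes first. Time to progression ends only at progression, and a subject who dies without it is censored.

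The treatment phase enrols a population in which such deaths are foreseeable: "Subject has relapsed (progressive disease) or is refractory to one or more prior therapies". Censoring a death treats that subject as having had the same future risk of progression as those still under observation, which is hard to defend in relapsed disease. If time to progression were reported under an objective worded as PFS, the result could look more favourable than the stated endpoint would. Duration of response has the same question when a responder dies without a progression scan.

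Leaving both terms in the plan also leaves a choice open until after the data are seen, in an open-label single-arm trial.

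**Working it through.** **1. The plan's own figures.** The documents give no figure for PFS or time to progression. The only quantified design is for the response rate: stop if 0 of 7 respond, fail if 3 or fewer of 18 respond. The probability of declaring success at true rate p is

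P(success) = Σ (x₁ = 1 to 7) Bin(x₁; 7, p) × P(X₂ ≥ 4 − x₁), with X₂ ~ Bin(11, p).

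- p = 0.30: 0.8000 (stated power 80%)
- p = 0.10: 0.0893 (stated one-sided level 0.089)

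Both reproduce, and neither PFS nor time to progression enters the formula. (The stated 0.13 for early stopping at a 30% rate does not reproduce, since 0.7⁷ = 0.082; that is a separate matter.)

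**2. The texts side by side.**

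| Place | Time-to-event variables named |
|---|---|
| Synopsis, Exploratory Objective 1 | PFS, duration of response |
| Section 5.3, objective and endpoints | PFS, duration of response |
| Section 9.1 | duration of response, time to progression |
| Section 11.2.1 | by reference to section 5: PFS, duration of response |

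Section 9.1 is the outlier.

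**3. Direction.** For the same subjects, suppose deaths without progression are events for PFS and are censored at the date of death for time to progression. The times are then identical and the second analysis has fewer events, so its Kaplan-Meier curve lies on or above the PFS curve. This rests on the conventional definitions; the available text defines neither term.

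**4. Size, as illustration only.** Let λp be the hazard of progression and λd the hazard of death without progression, both constant, and let f = λd / (λp + λd) be the share of first events that are such deaths.

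- Median PFS = ln 2 / (λp + λd)
- Median time to progression, deaths censored = ln 2 / λp
- Ratio = 1 / (1 − f)

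With an assumed median PFS of 4 months, the 6-month PFS rate is 2^(−6/4) = 35.4%. The 6-month rate for time to progression is 2^(−(6/4)(1 − f)).

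| f (assumed) | Ratio of medians | Median time to progression, months | 6-month rate |
|---|---|---|---|
| 5% | 1.05 | 4.2 | 37.2% |
| 10% | 1.11 | 4.4 | 39.2% |
| 20% | 1.25 | 5.0 | 43.5% |
| 30% | 1.43 | 5.7 | 48.3% |
| 40% | 1.67 | 6.7 | 53.6% |

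At f = 20%, median PFS values of 3 and 6 months would become 3/0.8 = 3.75 and 6/0.8 = 7.5 months. Neither f nor the median comes from the documents.

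**5. A death before week 8.** Whether this subject is analysed at all depends on the FAS rule. If death counts as endpoint data, the subject stays in and is an early PFS event. If it does not, the subject may be dropped from the FAS altogether, not merely censored. Changing the word in section 9.1 does not settle this case.

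**6. Whether every relevant death is captured.** Deaths are reported as serious adverse events (section 9.3), but that reporting ends 30 days after the last dose or before a new anticancer therapy (section 9.9). Survival follow-up is described only from progression. A subject who stops treatment without progression, is still being scanned, and dies after that window is not expressly covered.

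**The case against.** The strongest reply is that section 11.2.1 already settles the matter. It takes the efficacy endpoints from section 5, section 5.3 says PFS, and no text says time to progression will be reported instead. This largely stands. PFS is the better-supported reading, and the reply shows which section to correct. It does not remove the conflict, because section 11.2.1 does not mention or reconcile the wording in 9.1.

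A second reply is that the sentence in 9.1 lists what is assessed by RECIST, which dates progression and not death, so it may simply name the radiological part of PFS. That is plausible. It is also a reason to say so plainly.

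A third is that the definitions may exist elsewhere. Parts of the document are not available, including the rest of Appendix II after the baseline non-target lesions, and section 11 refers to a separate SAP. This stands: the lack of a PFS or duration-of-response definition in the available text is not counted here as an error.

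A fourth is that the illustrated shifts say nothing about this trial. For f between 10% and 30% and a 4-month median they run from 0.4 to 1.7 months, less than one 8-week scan interval (about 1.8 months), in at most 18 subjects. This also stands, and the figures show direction and scale only.

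**Conclusion.** The inconsistency is real but minor. Section 9.1 names time to progression; the synopsis, section 5.3 and, by reference, section 11.2.1 specify PFS. Overstatement would arise only if time to progression were reported in place of PFS, and its size cannot be computed from the documents. The ratios of 1.11 to 1.43 rest on assumed death shares of 10% to 30%, constant hazards and the conventional definitions.

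Three stronger conclusions might be inferred and are not supported:

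- That the plan will overstate disease control. The statistical section points to PFS.
- That a death before week 8 would necessarily be an early censored value. Under the FAS rule that subject may not be analysed at all.
- That all deaths needed for PFS are already collected. The follow-up text does not secure this for subjects who leave treatment without progression.

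The endpoint is exploratory and summarised descriptively. The response-rate design, its alpha and its power do not change.

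**What to change.** 1. In section 9.1, replace time to progression with PFS, defined as the time from first dose to RECIST 1.1 progression or death from any cause, whichever is first. End duration of response at progression or death on the same basis.
2. If time to progression is wanted, keep it as a separately labelled supportive variable.
3. In section 11.1.1, state that a death before the first post-baseline scan counts as post-baseline endpoint data for the FAS.
4. State in section 9.1 that deaths without prior progression are recorded as efficacy events, including those after the adverse-event reporting window.
5. Carry the same definitions into the SAP, with censoring rules for new anticancer therapy and missed scans if these are not already there.

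The cost is a few sentences and a check that the case report form captures deaths before progression. No extra subjects or scans are needed. The reported median may be slightly less favourable. Because the FAS also serves the tumor response analysis, item 3 would keep an early death in that denominator as a non-responder. It does not alter the two-stage design: the synopsis definition of an evaluable subject does not require a scan after baseline.
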